9.4 Evaluation during treatment

- 1. Update **medical history** prior to each cycle of chemotherapy. History to include concomitant medication changes and any signs and symptoms. Reportable adverse events must be recorded in AdvantageEDC. To be performed within 48 hours prior to or on first day of each cycle.
- 2. **Physical examination** prior to each cycle of chemotherapy. Examination to include performance status (Appendix 20.5). All subjects will be evaluated for clinical response by physical examination prior to receiving treatment on each cycle. The exam should occur within 2 days prior to the start of each cycle but may occur on Day 1 of cycle. Disease measurable by physical examination will be recorded in two dimensions if possible. To be performed within 48 hours prior to or on first day of each cycle.
- 3. **FDG-PET/CT**. Combined FDG-PET/CT or FDG-PET + CT scans with and without IV contrast are required for this study. If a patient has an allergy to IV contrast, a CT scan without contrast will be permitted.
 - Restaging evaluation by a full body FDG-PET/CT within Day 22-28 of Cycle 2 (i.e., 7-13 days after the Cycle 2 Day 15 doses of AVD-BV). If the CT portion of the PET/CT is a non-contrast CT, an additional CT scan with and without contrast must be obtained. Tumor measurements and SUVs must be

documented. A neck CT must be included if palpable neck nodes were present at baseline and a diagnostic CT is being performed.

- As the false positive rate of FDG-PET scans may be higher in the HIV population, a biopsy of an unexpected FDG-PET avid lesion is recommended but remains at the discretion of the investigator.
- 4. **PFT** with volumes, spirometry, DLCLO, and room air pulse oximetry will be performed after every 2 cycles, on day 1 of cycles 3 and 5, within 7 days of cycle initiation. The DLCO adjusted for hemoglobin must be greater than 70% predicted to continue with therapy.
- 5. Neuropathy evaluation by completing the FACT/GOG-neurotoxicity **questionnaire** at the beginning of each cycle. To be performed once within 48 hours prior to or on first day of each cycle (Appendix 20.6).
- 6. **CBC** with differential within 48 hours of day 1 and 15 of each cycle. Results of CBC must be known prior to treatment.
- 7. Serum chemistries within 48 hours of day 1 and 15 of each cycle: electrolytes (Na, K, Cl, bicarbonate, Ca, Mg, and phosphorus), glucose, blood urea nitrogen (BUN), creatinine, total bilirubin, alkaline phosphatase (ALP), LDH, total protein, albumin, AST and ALT. Results do not need to be known prior to treatment unless clinically indicated.
- 8. **CD4/CD8** count will be performed within 48 hours of cycle 2 and cycle 5 day 1 along with the CBC evaluation.
- 9. **HIV-1 RNA viral load**, assessed by any approved viral load assay at the local laboratory. This will be performed within 48 hours of cycle 2 and cycle 5 day 1 along with the CBC evaluation. (The HIV viral load assay must detect at minimum viremia >200 copies/mL to be consistent with the DHHS HIV treatment guidelines).

For patients with undetectable HIV viral at baseline: If the viral load rises above 200 copies per mL, HIV resistance testing will be required. Both viral load and resistance testing information must be shared in real time with the primary HIV provider if different from the protocol investigator. (The HIV viral load assay must detect at minimum viremia >200 copies/mL to be consistent with the DHHS HIV treatment guidelines).

10. **Serum pregnancy test** for women of childbearing potential will be performed per institutional guidelines during the study.

9.5 Follow-up assessments

The studies listed below will be repeated post-therapy within 6-8 weeks of the last treatment dose (6-8 weeks after Cycle 6 Day 15) and then every 3 months (+/- 7 days) thereafter for 2 years; every 6 months (+/- 7 days) for the third through the fifth years unless otherwise specified. All study subjects should be followed for up to 5 years after treatment discontinuation or until death if occurring before 5 years of treatment discontinuation. Patients who discontinue all protocol therapy after a CR or PR are followed for up to 5 years after treatment for recurrence and survival. Patients who discontinue protocol therapy due to disease progression or other reasons are followed for survival for up to 5 years after treatment discontinuation. No additional studies except follow up for survival are required after disease progression. In those instances in which a third party payer denies payment for some or all of these laboratory analyses, absence of these test results will not be considered a protocol violation.

- 1. Medical history.
- 2. Physical examination, including performance status (see Appendix 20.5,

Performance Status Scale), vital signs (weight, height, body surface area), neurological examination, and if possible, two dimensional measurement of all palpable, peripheral lymph nodes and measurement of other sites of disease present on physical exam.

- 3. At the conclusion of chemotherapy, a full body FDG-PET/CT scan will be done between 6-8 weeks post the final treatment dose, Cycle 6 Day 15. This will be the final FDG-PET/CT needed for the study. A combined FDG-PET/CT or FDG-PET + CT scans with and without IV contrast are required for the post- treatment scan. If a patient has an allergy to IV contrast, a CT scan without contrast will be permitted. As the false positive rate of FDG-PET scans may be higher in the HIV population, a biopsy of an unexpected FDG-PET avid lesion is recommended but remains at the discretion of the investigator.
- 4. **CT scan** with oral/IV contrast every 6 months for 5 years. To begin 6 months from the post treatment FDG- PET/CT scan, obtained 6-8 weeks post the final chemotherapy dose (See Section 9.5).
- 5. **PFT** with volumes, spirometry, DLCO and pulse oximetry for any patient with a DLCO corrected for hemoglobin \leq 70% during therapy. To be repeated at all post-treatment evaluations until normalization.
- 6. **Bone** marrow **biopsy** need only be performed to confirm a CR if positive at baseline (only once, within 8 weeks of the last treatment dose).
- 7. **CBC** with differential at all post treatment evaluations.
- 8. Serum chemistries: electrolytes (Na, K, Cl, bicarbonate, Ca, Mg, and phosphorus), glucose, blood urea nitrogen (BUN), creatinine, total bilirubin, alkaline phosphatase (ALP), LDH, total protein, albumin, AST and ALT at all post treatment evaluations.
- 9. **CD4 and CD8 cell** count beginning with the first follow up visit and every 3 months after treatment completion for one year.
- 10. **HIV-1 RNA viral load**, assessed by any approved viral load assay at the local laboratory beginning with the first follow up visit and every 3 months after treatment completion for one year. (The HIV viral load assay must detect at minimum viremia >200 copies/mL to be consistent with the DHHS HIV treatment guidelines).

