9.6 Early Discontinuation of Therapy

Subjects discontinuing therapy early (i.e., PD or stable disease, administrative reasons, subject non- compliance, etc.) will have a medical history update and complete physical examination. The examination will include performance status and blood drawn for the following studies within 1 month after treatment discontinuation, unless otherwise noted. See Section 12 for a list of reasons for study termination. Subjects will be followed for survival only for 5 years after the last date of treatment:

- **CBC** with differential.
- Serum chemistries: electrolytes (Na, K, Cl, bicarbonate, Ca, Mg, and phosphorus), glucose, blood urea nitrogen (BUN), creatinine, total bilirubin, alkaline phosphatase (ALP), LDH, total protein, albumin, AST and ALT.
- **CD4 and CD8 cell** count (do not repeat if done within 1 month from removal from treatment).
- **HIV-1 RNA viral load** to be evaluated at the local laboratory, do not repeat if done within 1 month from removal from treatment).

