13.0 CRITERIA FOR PREMATURE DISCONTINUATION OF THE STUDY

13.1 Premature withdrawal from trial intervention

After enrollment, subjects will be permanently withdrawn from study treatment for any of the following reasons. In the event of withdrawal from treatment, the reason for study treatment removal and the date the subject was removed must be documented in the Off Protocol Treatment Form in AdvantageEDCSM. See Section 9.6 on evaluations to be performed at early discontinuation of therapy.

- 1. Participants who experience a delay of over 7 days in cycle 1 will be removed from the study. For subsequent cycles, if two sequential doses of AVD + BV or AVD alone are held due to unresolved toxicity, leading to a treatment delay of an additional 2 weeks (i.e., 4 weeks between doses), the participant will be taken off protocol therapy. The participant will be followed for survival and may resume AVD treatment off study.
- 2. Severe toxicities as outlined in Section 10.6.1.
- 3. Progressive lymphoma at any time while on study.
- 4. Voluntary withdrawal.
- 5. The investigator has the right to remove subjects from study for clinical reasons which he or she believes to be life threatening or resulting in significant morbidity to the subject.
- 6. Any subject who develops HBV reactivation or acute Hepatitis B as defined by the reappearance of a previously suppressed hepatitis B surface antigen, a positive IgM hepatitis B core antibody, and a positive viral load. Any patient with Hepatitis B or C who has worsening liver function as defined by Section 10.6.2 will also be removed from study.
- 7. Any subject who on repeat PFT is found to have a DLCO when corrected for anemia less than 70%.
- 8. Subjects who become pregnant or breast-feed.
- 9. Subjects with progressive disease at the end of cycle 2 will be removed from study treatment, while patients with stable disease may be removed from the study treatment at the discretion of the local responsible investigator. Progressive or stable disease defined at cycle 2 will be based by CT criteria only, as FDG-PET has yet to be validated in HIV-associated HL.
- 10. If found by central pathology review to not have the diagnosis of HL.

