21.0 APPENDIXES

21.2 Appendix Schedule of Evaluations (study flow-chart)

	Treatment (W-2) Must be completed within 2 weeks prior to patient registration (D-7) To be performed within 7 days prior to first day of cycle (D-21) To be performed within 21 days prior to Cycle 1, Day 1 (D-28) To be performed no more than 28 days before enrollment. (H-48) To be performed within 48 hours of day 1 and 15 of every cycle.													ay of cycle	Follow-up			
Date (weeks or months)	Eligibility (Baseline) 6 weeks before C1D1	C1D1	C1D15	C2D1	C2D15	C2D22 -28	C3D1	C3D15	C4D1	C4D15	C5D1	C5D1 5	C6D1	C6D15	End of treatment 6 -8 w after C6D15	Early Treatment Discontinuatio n 1 m after discontinuation	Every 3 m 2 y (+/-7d)	Every 6 m 3 y (+/-7d)
Informed consent	Х																	
Medical history and physical examination	Х	X (h-48)		X (h-48)			X (h-48)		X (h-48)		X (h-48)		X (h-48)		Х	Х	Х	Х
FDG-PET/CT or FDG-PET + CT	X (D-28)					Х									Х			
CT scan with oral/IV contrast (d) To be done if the CT portion of the PET/CT is without contrast.	X (d)														Х		Every 6 m	Х
PFTs with volumes, spirometry, DLCO and pulse oximetry (b) To be performed only for patients with DLCO (corrected for hemoglobin) <70% during treatment until normalization.	Х						X (d-7)				X (D-7)				X (b)			
MRI of brain with and without IV gadolinium contrast	Х																	
MUGA or echocardiogram	Х																	

	Treatment																	
	(W-2) M	lust be	complet	ed with	in 2 weel	ks prior	to patie	nt regis	tration (D-7) To	be perfo	ormed v	vithin 7	days pri	or to first da	ay of cycle		
					(D-21)) To be	perform	ned with	in 21 da ore that	ays prio 28 day	r to Cycl vs before	e 1, Da	y 1 Dent				Follow-up	
				(1	(B-20) H-48) To	be per	formed	within 4	8 hours	of day	1 and 15	of ever	y cycle.					
Date (weeks or months)	Eligibility (Baseline) 6 weeks before C1D1	C1D1	C1D15	C2D1	C2D15	C2D22 -28	C3D1	C3D15	C4D1	C4D15	C5D1	C5D1 5	C6D1	C6D15	End of treatment 6 -8 w after C6D15	Early Treatment Discontinuatio n 1 m after discontinuation	Every 3 m 2 y (+/-7d)	Every 6 m 3 y (+/-7d)
FACT-GOG-neurotoxicity questionnaire	Х	X (h-48)		X (h-48)			X (h-48)		X (h-48)		X (h-48)		X (h-48)					
Bone marrow biopsy (a) Does not have to be repeated if bone marrow involvement by lymphoma already documented after bone marrow biopsy more than 6 weeks prior to registration (if+) Only need to perform to confirm CR is positive at baseline (only once, within 8 weeks of last treatment dose)	X(a)														X (if +)			

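### French protocol: the lung-function retest that 9.5 orders after a low DLCO is missing from the early-discontinuation pathway to which 9.4 and 13.1 lead

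*Combined protocol and SAP*

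**What the plan says.** All references are to the French (LYSARC) protocol unless stated. The AMC schedule of evaluations contains no PFT.

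- **On-treatment tests.** PFT is done at baseline (9.3 item 7). In 9.4 item 4 it "will be performed after every 2 cycles, on day 1 of cycles 3 and 5, within 7 days of cycle initiation".
- **Retest after treatment.** Section 9.5 item 5 asks for volumes, "spirometry, DLCO and pulse oximetry for any patient with a DLCO corrected for hemoglobin" at or below 70% during therapy, and adds: "To be repeated at all post-treatment evaluations until normalization".
- **Stopping rule, first form.** Section 9.4 item 4: "The DLCO adjusted for hemoglobin must be greater than 70% predicted to continue with therapy". Section 13.1 item 7 lists among the reasons for permanent withdrawal from study treatment: "Any subject who on repeat PFT is found to have a DLCO when corrected for anemia less than 70" per cent. The opening of 13.1 refers withdrawn patients to 9.6 for their evaluations.
- **Stopping rule, second form.** Inclusion criterion 17 (repeated in the synopsis), 9.3 item 7 and the pulmonary row of 10.6.2 require a DLCO above 70% to continue brentuximab vedotin. They do not mention the other drugs.
- **Early discontinuation.** Section 9.6 lists history, examination, blood count, chemistries, CD4/CD8 and viral load, with no PFT. It says: "Subjects will be followed for survival only for 5 years after the last date of treatment".
- **Flow chart (21.2).** The PFT row is marked at baseline, C3D1, C5D1 and end of treatment. The last mark carries the note "To be performed only for patients with DLCO (corrected for hemoglobin) <70% during treatment until normalization". The early-discontinuation cell is blank.
- **Synopsis, duration of study.** Participants removed for unacceptable adverse events are followed until the event resolves or stabilises.

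**The concern.** The finding that triggers the retest is also the finding that, under 9.4 and 13.1, takes the patient off treatment. Section 13.1 then names a visit that does not include the retest. A site working from 13.1, 9.6 and the flow chart would have no instruction to repeat the DLCO; a site working from 9.5 would.

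At stake is a safety follow-up that the protocol itself considers necessary: 9.5 and the flow-chart note both intend testing to go on until the value is normal. If sites follow different sections, recovery from a low DLCO will be recorded for some patients and not for others. No efficacy endpoint depends on it.

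**Working it through.** There is no stated figure to reproduce. The check is a cross-reading of the sections, followed by a comparison of the boundaries.

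**1. When a low value can arise.** The scheduled on-treatment tests are at C3D1 and C5D1. A low DLCO during therapy is therefore found at one of these two points, or on an unscheduled test.

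**2. What happens next, by reading.**

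| Reading | Source | Pathway | Is a PFT called for? |
|---|---|---|---|
| A: low DLCO ends study treatment | 9.4 item 4; 13.1 item 7 | 9.6 visit within 1 month, then survival only | Not in 9.6 or in the flow chart's early-discontinuation column; yes in 9.5 item 5 |
| B: low DLCO ends brentuximab vedotin only | Criterion 17; 9.3 item 7; 10.6.2 | AVD may continue to the end-of-treatment visit, 6-8 weeks after C6D15 | Yes, by 9.5 item 5 and the flow-chart mark |
| C: low DLCO counts as an unacceptable adverse event | Synopsis | Followed until resolved or stable | No test is named, and the text does not say that a low DLCO counts |

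The gap lies in reading A. Nothing in the text says that 9.5 item 5 overrides 9.6, or the reverse.

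**3. Whether 9.5 settles it.** Its opening says that patients who stop all protocol therapy after a CR or PR are followed for recurrence and survival, and that those who stop for progression or other reasons are followed for survival. A responder withdrawn for a low DLCO fits both sentences. Section 9.6 gives survival only, without that distinction.

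**4. Whether the blank early-discontinuation cell is only a table convention.** The CD4/CD8 and viral-load rows are marked in the end-of-treatment column, with repeats carried in their notes, and their follow-up columns are blank. Those rows do have a mark under early discontinuation; the PFT row does not. The convention therefore explains the blank follow-up columns for PFT but not the blank early-discontinuation cell.

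**5. The boundary.** Each rule applied to three values of DLCO:

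| DLCO | 9.4: continue only if >70% | 13.1: withdraw if <70% | 9.5: retest if <=70% | Flow chart: retest if <70% |
|---|---|---|---|---|
| 69% | stop | withdraw | retest | retest |
| 70% | stop | no withdrawal | retest | no retest |
| 71% | continue | no withdrawal | no retest | no retest |

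At exactly 70% the stopping rules disagree with each other, and so do the retest rules.

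**6. How many.** Section 7.0 expects 20 French participants among 51. The documents give no rate of DLCO decline, so the number affected lies somewhere from 0 to 20 and cannot be narrowed from the text.

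**The case against.** The strongest reply is that the plan offers other routes to the retest. Three passages limit the 70% rule to brentuximab vedotin, and 10.6.1 lets patients continue AVD after that drug is stopped in other circumstances. Such a patient reaches the end-of-treatment visit and is tested. The synopsis clause on adverse events may also cover a patient withdrawn for a low DLCO, and 9.5 item 5 is worded for any patient, not only for those who complete treatment. All of this stands. It shows that the omission is conditional on a reading; it does not remove the conflict, because 9.4 and 13.1 say something different and 13.1 names 9.6.

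A reader might infer more than the documents support:

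- **That the retest reaches almost nobody.** This needs reading A to be the only one, and readings B and C are in the text.
- **That the flow chart's blank follow-up columns contradict 9.5.** They do not. The PFT row follows the CD4/CD8 and viral-load rows, with the repeat instruction in the note ("during treatment until normalization").
- **That leaving completers with a DLCO above 70% untested after C5D1 undermines the toxicity objective.** The schedule does leave them untested. But 16.4 analyses toxicity as tabulated frequency and severity of adverse events, and no stated analysis uses DLCO. Not retesting patients with acceptable values is a design choice.

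**Conclusion.** The inconsistency is real and confined to the French protocol. If a low DLCO leads to withdrawal under 9.4 and 13.1, the patient is directed to a visit without the PFT that 9.5 orders, and may miss it. If the limit stops brentuximab vedotin only, or if the adverse-event clause is applied with a PFT, the retest can still take place. The documents do not say which reading governs.

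The size cannot be stated beyond the ceiling of 20 expected participants; any assumed percentage would have no basis in the text. The missing test does not enter the primary PFS estimate. The matter is still worth correcting, because it concerns a safety follow-up that the plan already requires and whose delivery now depends on which section a site reads.

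**What to change.** Reconcile 9.3, 9.4, 9.5, 9.6, 10.6.2, 13.1, inclusion criterion 17, the synopsis and the flow chart so that they agree on three things:

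1. what a low DLCO stops: all study treatment, or brentuximab vedotin only;
2. which follow-up pathway and PFT schedule then apply, including what is done at early discontinuation and how this fits with survival-only follow-up and the synopsis clause on adverse events;
3. one DLCO boundary, used in every place.

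Which clinical rule applies is for the sponsor to decide; this point asks only that the passages agree. The cost is a wording amendment, plus tests that 9.5 item 5 already orders. No change to sample size or analysis is needed.

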9.6 Early Discontinuation of Therapy

Subjects discontinuing therapy early (i.e., PD or stable disease, administrative reasons, subject non- compliance, etc.) will have a medical history update and complete physical examination. The examination will include performance status and blood drawn for the following studies within 1 month after treatment discontinuation, unless otherwise noted. See Section 12 for a list of reasons for study termination. Subjects will be followed for survival only for 5 years after the last date of treatment:

- **CBC** with differential.
- Serum chemistries: electrolytes (Na, K, Cl, bicarbonate, Ca, Mg, and phosphorus), glucose, blood urea nitrogen (BUN), creatinine, total bilirubin, alkaline phosphatase (ALP), LDH, total protein, albumin, AST and ALT.
- **CD4 and CD8 cell** count (do not repeat if done within 1 month from removal from treatment).
- **HIV-1 RNA viral load** to be evaluated at the local laboratory, do not repeat if done within 1 month from removal from treatment).

10.0 TREATMENTS

10.1 Treatment schedule and design

AVD dosing, in conjunction with brentuximab vedotin will be as described in Table 2. Drugs will be given on days 1 and 15 on a 28-day cycle for a total of 6 cycles. Brentuximab Vedotin will be administered after AVD (doxorubicin 25 mg/m², vinblastine 6 mg/m², dacarbazine 375 mg/m²).

If treatment is delayed (<7 days if during cycle 1, or <2 weeks if occurring during subsequent cycles) once treatment is resumed the next dose will be scheduled two weeks after treatment is restarted.

Doxorubicin	Vinblastine	Dacarbazine	Brentuximab Vedotin**	
Day 1, 15 Of 28-day cycle				
25 mg/m ²	6 mg/m ²	375 mg/m ²	1.2 mg/kg**	

Table 2: Schema for AVD-BV regimen*

*GCSF will be administered on Days 2-10 and 16-24 throughout each 28-day cycle using standard doses. Pegfilgrastim may be substituted on days 2 and 16. (See Section 10.10.1)

**For participants with weight exceeding 100kg, the dosage of Brentuximab Vedotin will be calculated based on a weight of 100kg. Maximal dose = 120 mg.

10.2 Radiation Therapy

Involved field radiotherapy should be given at the discretion of the investigator after chemotherapy if there was bulky (>10cm) disease at diagnosis as suggested in the NCCN guidelines. Radiation therapy initiation will be within 2 weeks after protocol therapy. Radiotherapy may be performed during the follow-up period according to institutional standards.

10.3 HAART

HAART is a requirement for the duration of the study. Patients must be on HAART therapy for at least 7 days before therapy. The specific agents are at the discretion of the Investigator. Protease Inhibitors and Integrase Inhibitors boosted with ritonavir or cobistat are contraindicated. Non-nucleosides reverse transcriptase (NNRTIs) are not recommended, however, in the absence of alternative therapy, their use will be discussed in the presence of a pharmacologist in the national "RCP" (réunion de concertation pluridisciplinaire) for patients with HIV associated lymphomas.

The sponsor will not provide the HAART as it is considered as standard care for HIV patients. HAART is to be used according to summary of product characteristics.

